### 7.1.5 Rechallenge

Reinitiation of intervention with the IMP will be done under close and appropriate clinical and/or laboratory monitoring once the Investigator will have considered according to his/her best medical judgment that the responsibility of the IMP(s) in the occurrence of the concerned adverse event

was unlikely and if the selection criteria for the study are still met (refer to [Section 5.1](#) and [Section 5.2](#)).

For a regional or national emergency declared by a governmental agency, contingency measures are included in Appendix 9 ([Section 10.9](#): Contingency measures for a regional or national emergency that is declared by a governmental agency).

## 7.2 PARTICIPANT DISCONTINUATION/WITHDRAWAL FROM THE STUDY

- A participant may withdraw from the study at any time at the participant's own request for any reason (or without providing any reason).
- A participant may be withdrawn at any time at the discretion of the Investigator for safety, behavioral, or compliance reasons.
- At the time of discontinuing from the study, if possible, an EOT Visit should be conducted, as shown in the SoA. See SoA for data to be collected at the time of study discontinuation and follow-up and for any further evaluations that need to be completed.
- If the participant withdraws consent from the study, the Sponsor will retain and continue to use any data collected before such a withdrawal of consent, as per applicable clinical regulation(s).
- If a participant withdraws from the study, the participant may request destruction of any samples taken and not tested, and the Investigator must document this in the site study records.

If participants no longer wish to take the IMP, they will be encouraged to remain in the study and to complete the safety follow-up.

The Investigators should discuss with them key visits to attend. The value of all their study data collected during their continued involvement will be emphasized as important to the public health value of the study.

Participants who withdraw from the study intervention should be explicitly asked about the contribution of possible AEs to their decision, and any AE information elicited must be documented.

All study withdrawals should be recorded by the Investigator in the appropriate screens of the eCRF and in the participant's medical records. In the medical record, at least the date of the withdrawal and the reason should be documented.

In addition, a participant may withdraw his/her consent to stop participating in the study. Withdrawal of consent for intervention should be distinguished from withdrawal of consent for Follow-up Visits and from withdrawal of consent for non-participant contact follow-up, eg, medical record checks. The site should document any case of withdrawal of consent.

Participants who have withdrawn from the study cannot be rerandomized/reallocated (treated) in the study. Their inclusion and intervention numbers must not be reused.

### **7.3 LOST TO FOLLOW-UP**

A participant will be considered lost to follow-up if the participant repeatedly fails to return for scheduled visits and is unable to be contacted by the study site.

The following actions must be taken if a participant fails to return to the clinic for a required study visit:

- The site must attempt to contact the participant and reschedule the missed visit as soon as possible, counsel the participant on the importance of maintaining the assigned visit schedule and ascertain whether the participant wishes to and/or should continue in the study.
- Before a participant is deemed lost to follow-up, the Investigator or designee must make every effort to regain contact with the participant (where possible, 3 telephone calls, and, if necessary, a certified letter to the participant's last known mailing address or local equivalent methods). These contact attempts should be documented in the participant's medical record.
- Should the participant continue to be unreachable, the participant will be considered to have withdrawn from the study.

## 8 STUDY ASSESSMENTS AND PROCEDURES

- Study procedures and their timing are summarized in the SoA. Protocol waivers or exemptions are not allowed.
- Adherence to the study design requirements, including those specified in the SoA, is essential and required for study conduct.
- All screening evaluations must be completed and reviewed to confirm that potential participants meet all eligibility criteria. The Investigator will maintain a screening log to record details of all participants screened and to confirm eligibility or record reasons for screening failure, as applicable.
- Procedures conducted as part of the participant's routine clinical management (eg, blood count, urine tests) and obtained before signing of the ICF may be utilized for Screening or Baseline purposes provided the procedures met the protocol-specified criteria and were performed within the timeframe defined in the SoA.
- In the event of a significant study-continuity issue (eg, caused by a pandemic), alternate strategies for participant visits, assessments, medication distribution and monitoring may be implemented by the Sponsor or the Investigator, as per local Health Authority/ethics requirements (see Appendix 9 [[Section 10.9](#)]).
- Safety/laboratory results that could unblind the study will not be reported to investigative sites or other blinded personnel until the study has been unblinded.

For a regional or national emergency declared by a governmental agency, contingency measures are included in Appendix 9 ([Section 10.9](#): Contingency measures for a regional or national emergency that is declared by a governmental agency).

### 8.1 ADMINISTRATIVE AND SCREENING/BASELINE PROCEDURES

[figure not shown]
#### 8.1.1 Inclusion and Exclusion Criteria

Participants will be evaluated to ensure they meet all inclusion criteria and none of the exclusion criteria at the Screening and Baseline Visits.

[figure not shown]
#### 8.1.2 Informed Consent

An Independent Ethics Committee (IEC)/Institutional Review Board (IRB) approved, study-specific informed consent will be reviewed, signed and dated by the participant before any study procedures are undertaken, or before any medications are withheld from the participant in order to participate in this study.

#### 8.1.3 Informed Consent for [REDACTED]

#### **8.1.4 Informed Consent fo [REDACTED]**

#### **8.1.5 Demographics**

Demographic information will be collected at the Screening Visit as follows:

- Age.
- Gender.
- Ethnicity.

#### **8.1.6 Medical and Surgical History (Includes Alcohol, Nicotine, and Substance Usage)**

At the Screening Visit, the Investigator will record significant medical or surgical events (including tonsillectomy) and be responsible for review of the medical history (including history of hypertension and/or diabetes) of participants to ensure that they meet the criteria for eligibility for the study. This will include a review of the study inclusion and exclusion criteria, which will be repeated at the Baseline Visit.

History of current prescription drug or substance abuse, including alcohol, considered significant by the Investigator is an exclusion criterion for this study (see [Section 5.2](#)). Drug abuse is a patterned use of a substance in which the participant uses amounts or methods that are harmful to themselves or others during the study period. If the medical history suggests such abuse, then the Investigator should consider whether the participant meets the exclusion criteria. Drugs of abuse screening, including breath test, may be performed at the Investigator's discretion. Tobacco use (duration of current or past use and quantity used) will also be documented but is not an exclusion criterion.

#### **8.1.7 Hidradenitis Suppurativa and Other Dermatologic History**

Detailed information of each participant's HS and other dermatologic history will be collected at the Screening Visit and will include, but will not be limited to, the following:

- The date of initial onset of HS.
- The date, onset, and duration of past treatments for HS.
- The date of any prior surgeries for HS.

- The presence of comorbid atopic dermatitis and psoriasis in HS participants as assessed by the Investigator through participant interview and review of medical history.

### **8.1.8 Family History of Hidradenitis Suppurativa**

Detailed information of each participant's family history of HS will be collected at the Screening Visit and will include whether the participant's first-degree relatives (ie, parent, sibling, or child of the participant) carry a physician-diagnosis of HS or experienced signs and symptoms consistent with a diagnosis of HS currently or in the past.

## **8.2 EFFICACY ASSESSMENTS**

Planned timepoints for all efficacy assessments are provided in the SoA.

### **8.2.1 Clinician Reported Outcome Measures**

#### ***8.2.1.1 Hidradenitis Suppurativa Clinical Parameters (HS Clinical Parameters)***

The HS Clinical Parameters are defined as a broad assessment of affected anatomic areas, lesions count in the respective areas, and characterization of intervening skin in the respective areas in HS participants. The HS Clinical Parameters must address all relevant anatomical regions in each participant. The parameters will include the following:

- Affected area (ie, left and right axilla, left and right sub/inframammary area, intermammary area, left and right buttock, left and right inguino-crural fold, perianal area, perineal area, or other area, as described in guidance provided to the Investigator).
- Lesion counts in each affected area. Types of lesions counted will be:
  - Abscess: a circumscribed collection of purulent exudate frequently associated with swelling and other signs of inflammation, such as fluctuance, tenderness and pain.
  - Non-inflammatory nodule: nontender or minimally tender, nonerythematous nodule.
  - Inflammatory nodule: a tender, erythematous, well-defined nodule; the lesion has no evidence of fluctuance. A pyogenic granuloma is considered an inflammatory nodule; a papule or pustule is not considered an inflammatory nodule.
  - Nondraining tunnel: a tunnel is a pathologic passageway connecting to the skin surface from dermis or subcutaneous tissue. A nondraining tunnel is a nontender or minimally tender, non-erythematous tunnel.
  - Draining tunnel: a tunnel that drains serous or purulent fluid, either spontaneously or by gentle palpation.
  - Hypertrophic scar: enlargement or overgrowth of a scar so that it extends above the surrounding skin surface.
- Hurley Stage assessment (see [Section 8.2.1.5](#)).

The HS Clinical Parameters will be assessed at the designated study visits according to the SoA (see [Section 1.3](#)). Appendix 11 ([Section 10.11.1](#)) provides a representative example of the HS Clinical Parameters that will be used in this study.

### **8.2.1.2 *Hidradenitis Suppurativa Clinical Response***

The Hidradenitis Suppurativa Clinical Response (HiSCR50) is a valid and meaningful endpoint for assessing HS treatment effectiveness in controlling inflammatory manifestations in this population (8). The HiSCR50 is defined as at least a 50% reduction from Baseline in the total abscess and inflammatory nodule count, with no increase from Baseline in abscess or draining tunnel count.

The HiSCR75 is defined as at least a 75% reduction from Baseline in the total abscess and inflammatory nodule count, with no increase from Baseline in abscess or draining tunnel count. The HiSCR90 is defined as at least a 90% reduction from Baseline in the total abscess and inflammatory nodule count, with no increase from Baseline in abscess or draining tunnel count.

The HiSCR50, HiSCR75, and HiSCR90 will be assessed at each of the prespecified times when the HS Clinical Parameters are scheduled to be assessed, at the designated study visits according to the SoA (see [Section 1.3](#)). The score will be calculated using data recorded for HS Clinical Parameters in the eCRF (see [Section 8.2.1.1](#)).

### **8.2.1.3 *International Hidradenitis Suppurativa Severity Score System (IHS4)***

The IHS4 is a validated tool to assess HS severity (32). The determination of IHS4 requires counting inflammatory nodules, abscesses and draining tunnels and multiplying each by a specific coefficient making it straightforward to apply in both research and clinical practice and easy to use in conjunction with the HiSCR50. A continuous IHS4 score can be derived based on this weighted score. A categorial IHS4 score can also be derived from the weighted score: a total score of 3 or less signifies mild, 4-10 signifies moderate, and 11 or higher signifies severe disease. A dichotomous score can also be derived, known as IHS4-55, which is defined as a 55% reduction in IHS4 score from Baseline (33).

The IHS4 will be assessed at each of the prespecified times when the HS Clinical Parameters are scheduled to be assessed, at the designated study visits according to the Schedule of Activities [Section 1.3](#). The score will be calculated using data recorded for HS Clinical Parameters in the eCRF (see [Section 8.2.1.1](#)).

### **8.2.1.4 *Abscess and Inflammatory Nodule (AN) Count***

The AN count is the sum of the abscess count and inflammatory nodule count at any given clinical assessment. It is derived from the lesion counts count obtained as part of the HS Clinical Parameters (see [Section 8.2](#)). It can be used to determine whether a participant is experiencing an HS disease flare, defined as at least 25% increase in AN count (with a minimum increase of 2) relative to Baseline.

### **8.2.1.5 *Hurley Stage***

The Hurley Stage is a severity classification for HS that was developed in 1989 and is widely used for the determination of the severity of HS. The Hurley Stage is defined by the following criteria:

- Stage I: Abscess formation (single or multiple) without sinus tracts and cicatrization.
- Stage II: Recurrent abscesses with tract formation and cicatrization; single or multiple, widely separated lesions.
- Stage III: Diffuse or near-diffuse involvement, or multiple interconnected tracts and abscesses across the entire area (34).

The Investigator will determine the Hurley Stage in each affected anatomical region at the designated study visits according to the SoA (see [Section 1.3](#)). Appendix 11 ([Section 10.11.1](#)) provides a representative example of the HS Clinical Parameters that will be used in this study in which the Hurley Stage is also included.

#### **8.2.1.6 *Hidradenitis Suppurativa Physician's Global Assessment (HS-PGA)***

The HS-PGA is a validated 6-point scale that is used to measure improvement in inflammatory nodules, abscesses, and draining fistulas (35). The HS-PGA scale is defined by the following:

- Clear: 0 abscesses, 0 draining fistulas, 0 inflammatory nodules, and 0 non-inflammatory nodules.
- Minimal: 0 abscesses, 0 draining fistulas, 0 inflammatory nodules, and presence of non-inflammatory nodules.
- Mild: 0 abscesses, 0 draining fistulas, and 1-4 inflammatory nodules OR 1 abscess or draining fistula and 0 inflammatory nodules.
- Moderate: 0 abscesses, 0 draining fistulas, and  $\geq 5$  inflammatory nodules OR 1 abscess or draining fistula and  $\geq 1$  inflammatory nodule OR 2-5 abscesses or draining fistulas and  $\geq 10$  inflammatory nodules.
- Severe: 2-5 abscesses or draining fistulas and  $\geq 10$  inflammatory nodules.
- Very severe:  $> 5$  abscesses or draining fistulas.

The HS-PGA will be assessed at the prespecified times when the HS Clinical Parameters are scheduled to be assessed, at the designated study visits according to the SoA (see [Section 1.3](#)). The score will be calculated using data recorded for HS Clinical Parameters in the eCRF (see [Section 8.2.1.1](#)).

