[REDACTED], components of the HiSCR50, disease flares, use of rescue therapy, Hidradenitis Suppurativa-Physician's Global Assessment (HS-PGA), quality of life (QoL) measures, and pruritus will be performed up to Week 28 in the biologic and small molecule immunosuppressive-naïve and TNF-experienced subgroups.

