**10.11.3 Hidradenitis Suppurativa Physician's Global Assessment (HS-PGA)**

---

|                |   |
|----------------|---|
| Clear   | 0 abscesses, 0 draining fistulas, 0 inflammatory nodules, and 0 non-inflammatory nodules.           |
| Minimal | 0 abscesses, 0 draining fistulas, 0 inflammatory nodules, and presence of non-inflammatory nodules. |

---

**Mild** 0 abscesses, 0 draining fistulas, and 1–4 inflammatory nodules OR 1 abscess or draining fistula and 0 inflammatory nodules.

**Moderate** 0 abscesses, 0 draining fistulas, and  $\geq 5$  inflammatory nodules OR 1 abscess or draining fistula and  $\geq 1$  inflammatory nodule OR 2–5 abscesses or draining fistulas and  $\geq 10$  inflammatory nodules.

**Severe** 2–5 abscesses or draining fistulas and  $\geq 10$  inflammatory nodules.

**Very Severe** >5 abscesses or draining fistulas.

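### HS-PGA: Moderate and Severe share a criterion, so a participant with 2-5 abscesses or draining fistulas gets either no grade or two

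*Protocol*

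**What the plan says.** Protocol 8.2.1.6 introduces the measure as follows: "The HS-PGA is a validated 6-point scale that is used to measure improvement in inflammatory nodules, abscesses, and draining fistulas". It then defines the six grades by lesion counts. Mild is "0 abscesses, 0 draining fistulas, and 1-4 inflammatory nodules OR 1 abscess or draining fistula and 0 inflammatory nodules". Moderate has three alternatives. The second and third run "inflammatory nodule OR 2-5 abscesses or draining fistulas and", followed by a threshold of at least 10 inflammatory nodules. The next grade is "Severe: 2-5 abscesses or draining fistulas and", followed by the same threshold. Appendix 10.11.3 restates the scale with the same duplication: "inflammatory nodule OR 2–5 abscesses or draining fistulas and", again with at least 10 nodules, and Severe again identical.

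On how the grade is obtained, 8.2.1.6 says: "The score will be calculated using data recorded for HS Clinical Parameters in the eCRF". The history of amendment 03 (10.12.3) gives the background: the HS-PGA was removed from the parameters to be rated because it would be derived.

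On its role, the Rationale in the synopsis lists it among additional exploratory analyses: "Hidradenitis Suppurativa-Physician's Global Assessment (HS-PGA), quality of life (QoL) measures, and pruritus will be performed up to Week 28", in both treatment-history subgroups. The visible SAP text does not define or mention the HS-PGA. The exploratory rows of SAP Table 2 and parts of SAP 2.4 are blacked out.

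**The concern.** A derived ordinal scale has to give each set of counts exactly one grade. Here two adjacent grades share a criterion, and the region that would separate them belongs to no grade. Since the grade is calculated, the written rule is the measurement, and no rating is collected that could fill the gap.

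The missing grades would not be random with respect to response:

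- A participant who goes from 6 abscesses (Very severe) to 3 abscesses with 4 inflammatory nodules improves and loses their grade.
- A participant with 3 abscesses who goes from 12 nodules to 8 moves from two grades to none.

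SAP 2.4.3 applies the methods of the secondary endpoints to exploratory endpoints at Week 16 in the naïve population. If the HS-PGA endpoint is a responder endpoint (its definition is not visible), an ungraded participant could then be imputed as a non-responder because of the gap rather than the disease. The alternative is that a programmer chooses a repair during the analysis, in which case the derivation was not prespecified.

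**Working it through.** No figure in the plan needs reproducing; the check is whether the six definitions partition the possible counts.

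**Inputs.** All criteria come from Protocol 8.2.1.6 and are identical in 10.11.3. Let L = abscesses plus draining fistulas, N = inflammatory nodules, M = non-inflammatory nodules.

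| Grade | Criterion as written |
|---|---|
| Clear | L = 0, N = 0, M = 0 |
| Minimal | L = 0, N = 0, M ≥ 1 |
| Mild | (L = 0 and 1 ≤ N ≤ 4) or (L = 1 and N = 0) |
| Moderate | (L = 0 and N ≥ 5) or (L = 1 and N ≥ 1) or (2 ≤ L ≤ 5 and N ≥ 10) |
| Severe | 2 ≤ L ≤ 5 and N ≥ 10 |
| Very severe | L > 5 |

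**Step 1: go through L.**

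- L = 0: N = 0 is Clear or Minimal according to M, N = 1-4 is Mild, N ≥ 5 is Moderate. One grade each.
- L = 1: N = 0 is Mild, N ≥ 1 is Moderate. One grade each.
- L = 2-5 and N = 0-9: no criterion applies.
- L = 2-5 and N ≥ 10: Moderate and Severe both apply.
- L > 5: Very severe only.

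**Step 2: count.** The ungraded region is 4 values of L by 10 values of N, so 4 x 10 = 40 combinations. The double-graded region has no upper limit on N, so its count depends on where the enumeration stops.

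A full enumeration over L = 0-20, N = 0-30 and M absent or present has 21 x 31 x 2 = 1302 profiles:

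- no grade: 40 x 2 = 80
- two grades, always Moderate and Severe: 4 x 21 = 84 combinations, and 84 x 2 = 168 profiles
- exactly one grade: 1302 - 80 - 168 = 1054

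**Step 3: does it depend on summing abscesses and fistulas?** The text does not say that the two are added. If the thresholds are applied to each lesion type separately, a grid of 0-6 abscesses, 0-6 fistulas and 0-14 nodules with M absent has 7 x 7 x 15 = 735 profiles. Of these, 240 have no grade, all with 0-9 nodules, and 160 are Moderate and Severe. New overlaps with Very severe also appear: 40 with Moderate and Severe, 28 with Moderate, 2 with Mild. Both defects remain and the definition gets worse.

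**Step 4: can participants be in this region?** Inclusion criteria I 06 and I 07 (Protocol 5.1) require an AN count of at least 3 and at most 20 draining tunnels at Baseline. A participant with 2 abscesses and 3 inflammatory nodules has an AN count of 2 + 3 = 5, meets both criteria, and has no HS-PGA grade.

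**Step 5: test the repair.** With the third alternative of Moderate changed to 2 ≤ L ≤ 5 and N < 10, all 1302 profiles have exactly one grade. Reversing the sign in Severe instead would also give one grade each, but would rank participants with fewer nodules above those with more. Of the one-symbol changes, only the change to Moderate keeps the grades in order.

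**The case against.** The textual defect is hard to dispute: the same threshold is printed in two separate places, so a single misread symbol in the PDF is unlikely. The case on the other side concerns weight and certainty.

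- **Low impact.** The HS-PGA is exploratory. It does not enter HiSCR, IHS4, flare, eligibility, stratification or the US Week 20 response rule. Protocol 9.2.4 calls exploratory analyses descriptive, and lesion counts are recorded whatever grade is derived, so it can be re-derived later. This stands and limits the weight of the point. SAP 2.4.3 does go beyond description at Week 16 in the naïve population.
- **Redacted SAP text.** A correct derivation may sit in the blacked-out parts of SAP 2.4. That is possible, so one cannot say that the analyses will be wrong, only that the protocol's rule cannot be followed as written. A correct SAP derivation would still contradict the protocol.
- **No evidence on frequency.** The 40 combinations are cells of a grid, not a share of participants. This stands: the region is open to enrolled participants, but how many fall in it is unknown.
- **The cut-off is inferred.** No text states fewer than 10 for Moderate, and other partitions exist, such as dropping the last alternative of Moderate together with the nodule condition of Severe. This stands as a reason to confirm the value. That alternative, however, takes two changes and removes a distinction the protocol draws.
- **Rated or calculated.** Footnotes bb (1.3.1) and cc (1.3.2) still describe the HS-PGA as an assessment performed with the clinical parameters. The same footnotes also list it among the derived measures, the parameter list in 8.2.1.1 omits it, and 8.2.1.6 says it is calculated. This is a small residual inconsistency and does not close the gap.

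**Conclusion.** The concern holds. As defined in Protocol 8.2.1.6 and 10.11.3, the HS-PGA gives no grade to 40 combinations (2-5 abscesses or draining fistulas, 0-9 inflammatory nodules) and two grades to every combination with 2-5 and 10 or more. The figure of 40 assumes that abscesses and fistulas are summed; the gap and the overlap persist without that assumption. The share of participants affected cannot be derived from the documents. The consequence is confined to an exploratory measure, and the primary HiSCR50 analysis and the secondary endpoints are untouched. The wording should be corrected before the HS-PGA is derived, but it does not threaten the trial's main conclusion.

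**What to change.** In Protocol 8.2.1.6 and 10.11.3, change the nodule threshold in the last alternative of Moderate from at least 10 to fewer than 10, after confirming it against the source cited for the scale. Put the same definition in the SAP derivation, state there that abscesses and draining fistulas are added together and that draining fistula means the draining tunnel counted under 8.2.1.1, and have the program check that every assessed visit receives exactly one grade.

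The cost is one symbol in two places and one line of the derivation, with no new data and no effect on treatment decisions. Protocol amendments need ethics committee approval under 10.1.1, so the SAP derivation can be fixed first and the protocol wording corrected at the next amendment.
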